2.1.3.5 Baseline

Baseline will be defined as the most recent non-missing value prior to the first dose of study treatment. For laboratory data, baseline will be defined as the most recent non-missing value from a laboratory prior to the first dose of study treatment.

If subjects have no value as defined above, the baseline results will be considered missing.

2.1.3.6 On-treatment assessment/event and observation periods

For adverse event reporting the overall observation period will be divided into three mutually exclusive segments:

1. **pre-treatment period:** from day of subject's informed consent to the day before first administration of study treatment
2. **on-treatment period:** from date of first administration of study treatment to 30 days after date of last actual administration of any study treatment (including start and stop date)
3. **post-treatment period:** starting at day 31 after last administration of study treatment.

2.1.3.7 Last contact date

The last contact date will be derived for subjects not known to have died at the analysis cut-off using the last complete date among the following:

Table 2-1 Last contact date data sources

Source data	Conditions
Last contact date/last date subject was known to be alive from Survival Follow-up page	Subject status is reported to be alive
Start/End dates from further antineoplastic therapy	Non-missing medication/procedure term.
Start/End dates from drug administration record	Non-missing dose. Doses of 0 are allowed.
End of treatment date from end of treatment page	No condition.
Tumor (RECIST) assessment date	Evaluation is marked as 'done'.
Laboratory/PK collection dates	Sample collection marked as 'done'.
Vital signs date	At least one non-missing parameter value
Performance Status date	Non-missing performance status

Source data	Conditions
Start/End dates of AE	Non-missing verbatim term

The last contact date is defined as the latest complete date from the above list on or before the data cut-off date. The cut-off date will not be used for last contact date, unless the subject was seen or contacted on that date. No date post cut-off date will be used. Completely imputed dates (e.g. the analysis cut-off date programmatically imputed to replace the missing end date of a dose administration record) will not be used to derive the last contact date. Partial date imputation is allowed for event (death)/censoring is coming from 'Survival information' eCRF.

The last contact date will be used for censoring of subjects in the analysis of overall survival.

2.2 Analysis sets

2.2.1 Analysis Populations

Full Analysis Set

The Full Analysis Set (FAS) comprises all subjects to whom study treatment has been assigned and who received one dose of study treatment.

Safety Set

The Safety Set includes all subjects who received any study treatment (i.e. at least one dose of any component of the study treatment).

FAS and Safety set are the same in this study.

2.2.2 Withdrawal of Informed Consent

Any data collected in the clinical database after a subject withdraws informed consent from all further participation in the trial, will not be included in the analysis. The date on which a subject withdraws full consent is recorded in the eCRF.

Death events may be used in the analysis if captured from public records (registers), local law and subject informed consent permitting.

Additional data for which there is a separate informed consent, e.g. PK, biomarker etc., collected in the clinical database without having obtained that consent will not be included in the analysis.

2.2.3 Subgroup of interest

Not applicable

2.3 Patient disposition, demographics and other baseline characteristics

All demographic, other baseline disease characteristics and medical history data were summarized and listed during primary analysis, and therefore will not be summarized in the final analysis.

2.3.1 Patient disposition

Subject disposition information will be listed and summarized based on FAS. The number (%) of treated subjects included in the FAS will be presented. The number (%) of subjects in the FAS who discontinued the study and the reason for discontinuation will be presented by mainland Chinese and all subjects.

The following summaries will be provided (with % based on the total number of FAS subjects):

- Number (%) of subjects who are still on-treatment (based on the both dabrafenib and trametinib ‘Study Treatment Discontinuation’ pages not completed)
- Number (%) of subjects who discontinued the study treatment phase (based on both dabrafenib and trametinib ‘Study Treatment Discontinuation’ pages)
- Primary reason for study treatment phase discontinuation (based on dabrafenib or trametinib ‘Study Treatment Discontinuation’ pages)

In addition, the number (%) of subjects who have discontinued from the post-treatment follow-up and the reasons for discontinuation from the post-treatment follow-up will be provided.

2.3.2 Protocol deviations

The number (%) of subjects in the FAS with protocol deviation will be tabulated by deviation category (as specified in the Protocol Deviation Management Plan) overall for the FAS. Major protocol deviations leading to exclusion from analysis sets will be tabulated separately by Mainland Chinese and all subjects. All the protocol deviations including the description will be listed.

The ongoing coronavirus disease 2019 (COVID-19) caused by severe acute respiratory syndrome coronavirus 2 (SARS-CoV-2) was first identified by the World Health Organization in Dec 2019. Since Mainland Chinese patients’ data from 01-Jul-2019 onwards are not included in the final analysis due to local regulations in China, and there were no COVID-19 related PDs for other patients, thus COVID-19 related PDs are not considered.

2.3.3 Analysis sets

The number (%) of subjects in each analysis set (defined in Section 2.2.1) will be summarized.

2.4 Treatments (study treatment, rescue medication, concomitant therapies, compliance)

2.4.1 Study treatment / compliance

2.4.1.1 Duration of study drug/treatment exposure

Extent of exposure to dabrafenib and trametinib will be summarized separately (see the details of duration of exposure below).

The duration of exposure to study treatment in months (from first day to last day of treatment) will be summarized. Descriptive statistics including mean, median, standard deviation, minimum, and maximum will be calculated for duration of exposure to study treatment. Moreover, duration of exposure to study treatment will be categorized in different time period: < 3 months, 3 months to 6 months, >6 months to 12 months, >12 months to 24 months, >24 months to 36 months and >36 months.

Duration of exposure to study treatment (*days*) = (last date of exposure to study treatment) – (date of first administration of study treatment) + 1.

The last date of exposure to study treatment is the last dates of exposure to investigational drug.

Duration of exposure by person time will be summarized by trametinib and dabrafenib. Person time of a specified group is defined as the total exposure time experienced by all subjects belonging to that specified group.

2.4.1.2 Cumulative dose

Cumulative dose for any component of study treatment (dabrafenib or trametinib) is defined as the total dose given during the study treatment exposure.

The **planned cumulative dose** for a study treatment component refers to the total planned dose as per the protocol up to the last date of investigational drug administration.

The planned cumulative dose is not summarized/listed. It is used for relative dose intensity calculations.

The **actual cumulative dose** refers to the total actual dose administered, over the duration for which the subject is on the study treatment as documented in the Dose Administration eCRF.

For subjects who did not take any drug the cumulative dose is by definition equal to zero.

The subject daily dose, defined as the cumulative dose divided by the duration of exposure for each subject will be summarized.

Subject level listings of all doses administered on treatment along with dose change reasons will be produced.

The safety set will be used for all summaries and listings of study treatment.

2.4.1.3 Dose intensity and relative dose intensity

The dose intensity (DI) and the relative dose intensity (RDI) for each study drug component (dabrafenib or trametinib) will be summarized by descriptive statistics. In addition, categorical

summary of RDI for each study drug component will be presented: <=75%, >75-90%, >90-110%, >110%.

Dose intensity (DI) for each study drug component in subjects with non-zero duration of exposure is defined as follows:

DI (dosing unit / day) = Actual Cumulative dose (dosing unit) / Duration of exposure to study treatment (day).

DI (mg/day) = Actual Cumulative dose (mg) / Duration of exposure (day)

For subjects who did not take any drug the DI is by definition equal to zero.

Planned dose intensity (PDI) is defined as follows:

PDI (dosing unit / day) = Planned Cumulative dose (dosing unit) / Duration of exposure (day).

Relative dose intensity (RDI) is defined as follows:

RDI = DI (dosing unit / day) / PDI (dosing unit / day).

DI and RDI will be summarized for each of the study treatment components.

The following tables provide the examples for the calculations, however, the final numbers should be based on the actual data, not from the following tables.

Table 2-2 Examples of dabrafenib dose administration and exposure

DAR record number	Start/End Date	Dose Prescribed (mg), frequency	Dose Administered (mg) [total daily]	Dose Changes, Dose Interruption	Dose Permanently Discontinued	Reason
1	01Jan2016 / 05Jan2016	150 mg BID	300	No	No	
2	06Jan2016 / 03Feb2016	150 mg BID	200	Yes	No	AE
3	04Feb2016 / 25Feb2016	150 mg BID	300	No	No	

Duration of exposure (days) = 25Feb2016 – 01Jan2016 + 1 = 56 days

Planned cumulative dose (for 56 days) = 300*56 = 16800 mg

Actual cumulative dose = 300*5 + 200*29 + 300*22 = 13900 mg

Dose intensity = 13900 mg / 56 days = 248.21 mg/day

Planned dose intensity = 16800 mg / 56 days = 300 mg/day

Relative dose intensity = DI / PDI = (248.21 mg/day) / (300 mg/day) = 0.83

Table 2-3 Examples of trametinib dose administration and exposure

DAR record number	Start/End Date	Dose Prescribed (mg), frequency	Dose Administered (mg) [total daily]	Dose Changes, Dose Interruption	Dose Permanently Discontinued	Reason
1	01Jan2016 / 10Jan2016	2 QD	2	No	No	
2	11Jan2016 / 15Jan2016	2 QD	0	Yes	No	AE
3	16Jan2016 / 25Feb2016	1 QD	1	No	No	AE

Duration of exposure = 25Feb2016 – 01Jan2016 + 1 = 56 days

Planned cumulative dose (for 56 days) = 2*56 = 112 mg

Actual cumulative dose = 2*10 + 0*5 + 1*41 = 61 mg

Dose intensity = 61 mg / 56 days = 1.09 mg/day

Planned dose intensity = 112 mg / 56 days = 2 mg/day

Relative dose intensity = DI / PDI = (1.09 mg/day) / (2 mg/day) = 0.54

2.4.1.4 Dose reductions, interruptions or permanent discontinuations

The number of subjects who have dose reductions, permanent discontinuations or interruptions, and the reasons, will be summarized separately for each of the study treatment components.

‘Dose interrupted’, and ‘Dose permanently discontinued’ fields from the Study Treatment CRF pages (DAR) will be used to determine the dose reductions, dose interruptions, and permanent discontinuations, respectively.

The corresponding fields ‘Reason for dose change/dose interrupted’ and ‘Reason for permanent discontinuation’ will be used to summarize the reasons.

A dose change is either ‘change in prescribed dose level’ or ‘dosing error’ where actual dose administered/total daily dose is different from the prescribed dose.

For the purpose of summarizing interruptions and reasons, in case multiple entries for interruption that are entered on consecutive days with different reasons will be counted as separate interruptions. However, if the reason is the same in this mentioned multiple entries on consecutive days, then it will be counted as one interruption.

Reduction: A dose change where the prescribed dose level is lower than the previous prescribed dose level or where the actual dose administered/total daily dose is lower than the calculated dose amount based on the prescribed dose. Therefore any dose change to correct a dosing error will not be considered a dose reduction. Only dose change is collected in the CRF, number of reductions will be derived programmatically based on the change and the direction of the change.

A listing of actual treatments will be produced.

In addition, summaries of study treatment exposure and dose modifications (e.g. number of dose reductions, number of dose interruptions) will further characterize compliance. These analyses are described in Section 2.4.1

2.4.2 Prior, concomitant and post therapies

2.4.2.1 Prior anti-cancer therapy

The number and percentage of subjects who received any prior anti-neoplastic medications, prior anti-neoplastic radiotherapy or prior anti-neoplastic surgery was summarized in primary analysis and therefore will not be summarized in the final analysis.

2.4.2.2 Post treatment anti-cancer therapy

Anti-neoplastic therapies since discontinuation of study treatment will be listed and summarized by ATC class, preferred term, overall and by means of frequency counts and percentages using FAS.

2.4.2.3 Concomitant medications

Concomitant therapy is defined as all interventions (therapeutic treatments and procedures) other than the study treatment administered to a subject coinciding with the study treatment period. Concomitant therapy include medications (other than study drugs) starting on or after the start date of study treatment or medications starting prior to the start date of study treatment and continuing after the start date of study treatment.

Concomitant medications will be coded using the World Health Organization (WHO) Drug Reference Listing (DRL) dictionary that employs the WHO Anatomical Therapeutic Chemical (ATC) classification system and summarized by lowest ATC class and preferred term using frequency counts and percentages. Surgical and medical procedures will be coded using MedDRA and summarized by SOC and preferred term. These summaries will include:

1. Medications starting on or after the start of study treatment but no later than 30 days after start of last dose of study treatment and
2. Medications starting prior to start of study treatment and continuing after the start of study treatment.

All concomitant therapies will be summarized. Any concomitant therapies starting and ending prior to the start of study treatment or starting more than 30 days after the last date of study treatment will be included. The safety set will be used for all concomitant medication tables and listings.

2.5 Analysis of the primary objective

The primary objective is to demonstrate the antitumor activity of dabrafenib in combination with trametinib as measured by ORR in subjects with BRAF V600 mutation-positive melanoma.

2.5.1 Primary endpoint

The primary endpoint, ORR is defined as the percentage of subjects, who have a confirmed complete response or a partial response based on RECIST 1.1 (Eisenhauer, 2009) and are evaluated by the investigator, among all subjects who have been enrolled and received at least one dose of investigational product. Tumor assessments performed before the start of any further antineoplastic therapy (i.e. any additional secondary antineoplastic therapy or surgery) will be considered in the assessment of overall response. Confirmation assessments must be performed no less than four weeks (28 days) after the criteria for response have initially been met and may be performed at the next protocol scheduled assessment. If a confirmation assessment is performed prior to the next protocol schedule assessment, the next protocol scheduled evaluation is still required.

ORR is defined as the proportion of subjects with confirm response of complete response (CR) or partial response (PR) according to RECIST 1.1. ORR will be calculated based on the FAS using local investigators review of tumor assessment data. Subjects with only non-measurable disease at baseline will be part of the analysis and will be included in the numerator only if a complete response was observed.

2.5.2 Statistical hypothesis, model, and method of analysis

The study will pursue an estimation strategy rather than formal hypothesis testing. This is reasonable given the proven performance of the combination therapy and the desire to estimate the effect in the Asian population. Since estimation is the goal, there are no formal hypotheses to be tested. 95% confidence limits for objective response rate (ORR) will be calculated. The minimal effect to be excluded from the lower end of the confidence interval for ORR will be 25%.

The primary objective was supported by the calculation of objective response rate using the FAS population. The primary analysis of ORR was performed after all enrolled subjects have completed 16 weeks of treatment or have at least 2 tumor assessments or have otherwise discontinued study treatment. The final analysis of ORR will be performed after LPLV.

The final efficacy analysis ORR will be summarized using descriptive statistics (N, %) along with 2-sided exact 95% confidence interval (CI) [Clopper and Pearson 1934].

2.5.3 Handling of missing values/censoring/discontinuations

Subjects with unknown or missing response will be treated as non-responders, i.e. they will be included in the denominator when calculating the percentage. No imputation will be performed for missing lesion assessments or tumor response data.

Subjects with unknown or missing best overall response (BOR) will be counted as failures. If there is no baseline tumor assessment, all post-baseline overall lesion responses are expected to be 'Unknown'. If no valid post-baseline tumor assessments are available, the best overall response must be "Unknown" unless progression is reported. For the computation of ORR, these subjects will be included in the FAS and will be counted as 'failures'.

2.5.4 Supportive analyses

Not applicable

2.6 Analysis of the key secondary objective

There is no key secondary objective in this study.

2.7 Analysis of secondary efficacy objective(s)

The other secondary efficacy objectives are to describe PFS, OS, and DOR.

2.7.1 Secondary endpoints

Progression-Free Survival (PFS)

PFS is defined as the time from the date of the first dose to the date of the first documented progression or death due to any cause. PFS will be based on local investigators review of tumor assessments and using RECIST 1.1 criteria. The analysis will be based on FAS and will include all data observed up-to the cut-off date.

In the final analysis, PFS will be censored at the date of the last adequate tumor assessment if no PFS event is observed prior to the analysis cut-off date or before the start of the new anticancer therapy date or loss to follow up, whichever is earlier. (See Section 2.7.3 for additional details regarding censoring rules and determination of date of last adequate tumor assessment). Discontinuation due to disease progression (collected on the 'End of treatment' and 'End of post treatment follow up' disposition pages) without supporting objective evidence satisfying progression criteria per RECIST 1.1 will not be considered disease progression for PFS derivation. Clinical deterioration will not be considered as a qualifying event for progression for the final analysis.

Overall Survival (OS)

Overall Survival (OS) is defined as the time from date of first dose to date of death due to any cause. A cut-off date will be established for each analysis of OS. All deaths occurring on or before the cut-off date in the FAS will be used in the OS analysis.

If a subject is not known to have died at the time of analysis cut-off, OS will be censored at the date of last contact (See Section 2.1.1.7 for additional details). The survival distribution of OS distribution will be estimated using the Kaplan-Meier method, and Kaplan-Meier curves, medians and 95% confidence intervals of the medians intervals.

Duration of Response (DOR)

Duration of response (DOR) only applies to subjects whose confirmed overall response is complete response (CR) or partial response (PR) according to RECIST 1.1 based on local investigators review of tumor assessment data. The start date is the date of first documented response of CR or PR (i.e., the start date of response, not the date when response was confirmed), and the end date is defined as the date of the first documented progression or death. Subjects continuing without progression or death due to underlying cancer will be censored at the date of their last adequate tumor assessment using the censoring rule described for PFS analysis (See Section 2.7.3 for additional details).

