2.7.3 Handling of missing values/censoring/discontinuations

For subjects who have not progressed or died at the time of the PFS or DOR analysis, censoring will be performed using the rules described in Table 2-4 or first dose for subjects without any adequate post baseline assessments.

PFS will be censored at the last adequate tumor assessment if one of the following occurs: absence of event; the event occurred after two or more missing tumor assessments. The term “missing adequate tumor assessment” is defined as a tumor assessment (TA) not performed or tumor assessment with overall lesion response of “UNK”. The rule to determine number of missing TAs is based on the time interval between the date of last adequate tumor assessment and the date of an event. If the interval is greater than twice the protocol-specified interval between the TAs and 2 times the protocol-allowed time window around assessments, then the number of missing assessments will be 2 or more.

If there is no adequate baseline assessment, the subject will be censored at their date of the first dose. Subjects without any adequate post baseline tumor assessments will be censored at the date of the first dose. Subjects who progressed or died after an extended period without adequate assessment will be censored at their date of last adequate assessment prior to progression or death even if subsequent information is available regarding progression or death. An adequate assessment is defined as an assessment where the investigator determined response is CR, PR, or SD. The date of response at that assessment will be used for censoring. As the assessment schedule changes through the course of the protocol (i.e. every 8 weeks until week 56 and then every 12 weeks thereafter), the following rules will be used for identifying extended loss to follow up or extended time without an adequate assessment (i.e. two or more missed assessments).

- If death or PD is on or prior to day 399 (week 56 + 7 day window), then a subject will be identified as an extended loss to follow up if the subject did not have an adequate

assessment during the time period of 119 days (16 weeks + 7 day window) prior to death or PD;

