- Else if death or PD is after day 399 (week 56 + 7 day window) and prior to day 567 (week 80 + 7 day window), then a subject will be identified as an extended loss to follow up if the subject did not have an adequate assessment during the time period of 147 days (8 weeks + 12 weeks + 7 day window) prior to death or PD.
- Else if death or PD is after day 567 (week 80 + 7 day window), then a subject will be identified as an extended loss to follow up if the subject did not have an adequate assessment during the time period of 175 days (24 weeks + 7 day window) prior to death or PD.

For subjects who receive subsequent anti-cancer therapy the following rules will apply:

- If the start date of the anti-cancer therapy is partial (i.e. either missing the day but has the month and year available or missing both day and month), the imputation rules described in Section 5.1 will be applied. No imputation will be made for completely missing dates.
- If anti-cancer therapy is started without documented disease progression or is started prior to documented disease progression, then PFS will be censored at the date of the last adequate assessment that is no later than the date of initiation of anti-cancer therapy (i.e. if an assessment occurs on the same day as the start of new anti-cancer therapy the assessment will be used - as it will be assumed the assessment occurred prior to the administration of new anti-cancer therapy). The date of response at the last adequate assessment will be used as the censoring date.
- If a subject has only a baseline visit or does not have an adequate assessment that is no later than the date of initiation of anti-cancer therapy, PFS will be censored at the date of the first dose.

Refer to [Table 2-4](#) for censoring and event date options and outcomes for PFS.

Table 2-3 Outcome and event/censor dates for PFS analysis

Situation	Date	Outcome
No baseline assessment	Date of the first dose	Censored
Progression or death at or before next scheduled Assessment	Date of progression (or death)	Progressed
Progression or death after exactly one missing assessment	Date of progression (or death)	Progressed
Progression or death after two or more missing assessments	Date of last adequate assessment prior to missed assessment	Censored
No progression (or death)	Date of last adequate assessment	Censored
Treatment discontinuation due to 'Disease progression' without documented progression, i.e.	Date of last adequate assessment	Censored

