Situation	Date	Outcome
clinical progression based on investigator claim		
New anticancer therapy given prior to protocol defined progression	Date of last adequate assessment on or prior to starting new anti-cancer therapy (or crossover treatment)	Censored
Death before first PD assessment (including death at baseline or prior to any adequate assessments)	Date of death	Progressed

Overall survival (OS)

If a subject is not known to have died at the time of analysis cut-off, then OS will be censored at the date of last known date subject was alive, i.e., last contact date (see [Table 2-1](#)).

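### The SAP's duration-of-response censoring sentence limits death to cancer death, while the protocol and the rest of the SAP count death from any cause

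*SAP*

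**What the plan says.** SAP 2.7.1 (Duration of Response) sets the event first: "the end date is defined as the date of the first documented progression or death". No cause of death is named. The next sentence gives the censoring rule: "Subjects continuing without progression or death due to underlying cancer will be censored at the date of their last adequate tumor assessment". That sentence then hands over to the PFS rule for the details.

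The rule it refers to, in SAP 2.7.3, opens with: "For subjects who have not progressed or died at the time of the PFS or DOR analysis, censoring will be performed". The PFS outcome table in that section counts as events, whatever the cause, "Progression or death after exactly one missing assessment" and "Death before first PD assessment (including death at baseline or prior to any adequate assessments"). It censors "Progression or death after two or more missing assessments" and "New anticancer therapy given prior to protocol defined progression".

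Protocol Table 1, 7.2.1.2 and 9.3.5.1.2 all end DOR at progression or death from any cause. Protocol 9.3.5.1.2 adds that DOR is to be censored by the PFS rules. SAP Table 1-1 repeats the any-cause definition. SAP section 4 lists two departures from the protocol (the renaming of the analysis population and the data cut-off for Mainland Chinese patients), and neither concerns DOR.

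**The concern.** A censoring sentence decides which follow-up times count as events. Under this one, a responder who dies of something other than melanoma, with no progression recorded, has not had the cancer death it names. That responder is censored at the last adequate scan, as if the response were still ongoing then. Under the protocol the response ended on the day of death.

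A death from a treatment-related serious adverse event would be handled this way, so the literal rule removes treatment-related deaths from a measure of how long benefit lasts. Within one report, the same death could count as a PFS event but not as a DOR event. The outputs at stake are the median DOR with its confidence interval (SAP 2.7.2) and any Kaplan-Meier estimates of DOR at fixed times (SAP 5.4.2).

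**Working it through.** **Step 1: the statements side by side.**

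| Place | Death that ends DOR |
|---|---|
| Protocol Table 1 | any cause |
| Protocol 7.2.1.2 | any cause |
| Protocol 9.3.5.1.2 | any cause; censoring as for PFS |
| SAP Table 1-1 | any cause |
| SAP 2.7.1, DOR end date | death, no cause given |
| SAP 2.7.1, DOR censoring | cancer death only |
| SAP 2.7.3, lead-in for PFS and DOR | died, no cause given |
| SAP 2.7.3, outcome table | death, no cause given |
| SAP 4, changes | none for DOR |

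One statement differs from all the others, and it is not declared as a change.

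**Step 2: can the literal rule be programmed?** Yes. SAP 2.8.2 classifies primary cause of death as disease under study, treatment-related SAE, or other.

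**Step 3: one responder under each rule.** Take a non-cancer death with no progression, at most one missed scan and no new anticancer therapy. Under SAP 2.7.3 this is an event on the date of death. Under the literal sentence it is censored at the last adequate scan. After two or more missed scans, or after new therapy, both rules censor and there is no difference.

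**Step 4: size (illustration only).** The documents give no expected DOR and no number *k* of such deaths, so there is no plan figure to reproduce.

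- Responders: 65 × 0.64 = 41.6, about 42. The 64% is the combination-arm response rate of the phase III comparison with vemurafenib (Protocol 1.2.3).
- Assumed true median DOR: 12 months, exponential.
- Set-up A: censoring uniform on 24 to 40 months (assumed), giving 35.1 events on average; each recoded death is censored 0 to 8 weeks earlier.
- Set-up B: scans every 8 weeks to week 56, then every 12 weeks (SAP 2.7.3), and response at week 8 (assumed). Minimum follow-up takes 16 weeks before 23-Feb-2018, that is 3-Nov-2017, as the latest first dose. From there it is 19.8 months to 30-Jun-2019 and 41.5 months to 19-Apr-2021, or 18.0 and 39.7 months from week 8. Upper limits of 36 and 58 months and a Mainland Chinese share of 60% or 100% are assumed.

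SAP 5.4.2 names the procedure but not how the median is read when the curve S equals exactly 0.5, so both conventions are shown. Mean shift in the Kaplan-Meier median, in months:

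| | Midpoint at S = 0.5 | First time S ≤ 0.5 |
|---|---|---|
| A, *k* = 1 | +0.25 | +0.50 |
| B, *k* = 1 (60%, 100%) | +0.29, +0.34 | +0.55, +0.63 |
| A, *k* = 2 | +0.71 | +1.06 |
| B, *k* = 2 (60%, 100%) | +0.78, +0.89 | +1.15, +1.25 |

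The sampling SD of the median is 2.6 to 2.9 months. With *k* = 1 the median is unchanged in 27% to 40% of runs. With the midpoint convention it is shorter in 3% to 4% (by at most 1.3 months), because the censoring date falls before the death. The 12-month estimate rises by about 0.009 to 0.010 per such death. With true medians of 9 and 15 months (set-up B, 100%, *k* = 1) the shifts are +0.19 and +0.51 (midpoint) or +0.40 and +0.74 (first time).

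**Step 5: cross-check by formula.** Under a constant hazard, if a share *f* of events is recoded as censored, the median is multiplied by 1/(1 − *f*). For *f* = 2%, 5% and 10% this gives 1.020, 1.053 and 1.111; a separate simulation with a 10-month median gave 1.019, 1.049 and 1.103. For *k* = 1, *f* = 1/35.1 = 0.0285, so 12 × (1/0.9715 − 1) = +0.35 months, inside the simulated range.

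**The case against.** The strongest reply is that SAP 2.7.1, read as a whole, already reaches the protocol rule. The end date is any death, a dead responder is not naturally described as continuing, and the disputed sentence hands over to 2.7.3, where cause plays no part. No DOR passage names a cause-of-death field or says how an unknown cause is treated, which suggests leftover wording rather than a chosen analysis. Much of this stands: a programmer who works from 2.7.3 gets the right answer, and the text does not prove which analysis will be run. But if only living subjects are meant, the words about cause of death do nothing. One reading departs from the protocol and the other leaves the phrase without a purpose, so it needs correcting either way.

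A second objection is that the illustration is more precise than its inputs, and this is fair. The midpoint figure depends on 42 being an even number: in set-up A, 41 or 43 responders give about +0.5 months under the midpoint convention too, with no shortened medians. Those values stay inside the overall range. The finding rests on the text and not on the simulation.

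**Conclusion.** The concern holds. Followed as worded, the sentence censors an event that the protocol defines as ending the response. If no responder died of a non-cancer cause without progression, nothing changes. If one did, the median DOR is usually unchanged or longer, by roughly a quarter to two-thirds of a month on average, given about 42 responders and a 12-month median. That is small against the sampling error, and the estimate rests on assumed follow-up, response timing and median. The endpoint is a descriptive secondary one with no hypothesis test. This is a definite wording error of limited consequence that should be corrected.

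**What to change.** In the DOR censoring sentence of SAP 2.7.1, replace *underlying cancer* with *any cause*. Keep the cross-reference to 2.7.3, so that the missed-assessment and new-therapy rules still apply to DOR as they do to PFS.

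SAP section 1 places its decisions before database lock. If lock has passed, confirm which rule was programmed, record the correction in the clinical study report, and state how many responders died of a non-cancer cause without progression.

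The cost is two words. If the literal rule was programmed, one derivation and its outputs must be re-run, and the reported DOR may be slightly less favourable.
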